4.2 OTHER TREATMENTS, EMERGENCY PROCEDURES, RESTRICTIONS

4.2.1 Other treatments and emergency procedures

There are no special emergency procedures to be followed.

Stable doses of concomitant therapies for chronic conditions, for which neither the condition nor the treatment are judged to exclude the patient from participation (See [Section 3.3](#)) are permissible. All concomitant medications should be carefully evaluated by the investigator and the CML should be contacted when there are questions regarding concomitant medications.

In the event that a patient experiences an intolerable increase of psoriasis, as deemed by the investigator, during the course of the trial the patient will be discontinued from the trial to receive rescue treatment.

In case of AEs in need of treatment symptomatic therapy according to investigator judgment will be permitted. All concomitant and/or rescue therapies will be recorded on the appropriate pages of the eCRF.

4.2.2 Restrictions

4.2.2.1 Restrictions regarding concomitant treatment

The medications (or classes of medications) listed in [Table 4.2.2.1: 1](#) must not be taken for the time periods as specified.

Table 4.2.2.1: 1 Restricted medications

Medication or class of medications	Restriction duration (through EOO Visit)
guselkumab , tildrakizumab	not allowed prior or during trial participation
briakinumab, ustekinumab (sterala [®]), secukinumab (Cosentyx [®])	6 months prior to randomisation
Brodalumab (Lumicef [®]), ixekizumab (Taltz [®])	4 months prior to randomisation
adalimumab (Humira [®]) , infliximab (Remicade [®]) investigational products for psoriasis (non-biologics)	12 weeks prior to randomisation
etanercept (Enbrel [®]) live virus vaccinations	6 weeks prior to randomisation
any investigational device or product (excludes psoriasis products) other systemic immunomodulating treatments (e.g., methotrexate, cyclosporine A, corticosteroids ¹ , cyclophosphamide, tofacitinib (Xeljanz [®]), apremilast) other systemic psoriasis treatments (e.g., retinoids, fumarates, any other drug known to possibly benefit psoriasis) photochemotherapy (e.g., PUVA)	30 days prior to randomisation
phototherapy (e.g., UVA, UVB) topical treatment for psoriasis or any other skin condition (e.g., corticosteroids ² , vitamin D analogues, vitamin A analogues, retinoids, salicylvaseline, salicylic acid, lactic acid, tacrolimus, tar, urea, α -hydroxy [fruit acids])	14 days prior to randomisation

¹ No restriction on corticosteroids with only a topical effect for non-skin indications (e.g., inhalative corticosteroids to treat asthma or corticosteroid drops used in the eye or ear).

² Exception: Topical steroids of medium such as Locoid or weak such as prednisolone for use on the face, axilla, and/or genitalia with a restriction of use within 24 hours prior to trial visit in which PASI is assessed.

4.2.2.2 Restrictions on diet and life style

Patients should be fasted for at least 8 hours prior to collection of the safety laboratory samples, starting from Visit 2. Moisturizers/emollients containing retinoids and the use of tanning beds are not allowed during the study.

4.2.2.3 Restrictions regarding women of childbearing potential

Female patients of childbearing potential should use the contraception methods described in [Section 3.3.2](#) and the patient information.

4.3 TREATMENT COMPLIANCE

Study medication will be administered in accordance with the protocol by authorised study personnel (e.g., investigators and study nurse). The measured plasma concentrations will provide additional information about compliance.

5. VARIABLES AND THEIR ASSESSMENT

5.1 TRIAL ENDPOINTS

5.1.1 Primary Endpoint

The primary endpoints in this trial is the achievement of $\geq 90\%$ reduction from baseline PASI score (PASI 90) at Week 16

5.1.2 Secondary Endpoints

Secondary Endpoints are:

- Achievement of $\geq 90\%$ reduction from baseline PASI score (PASI 90) at Week 52
- Achievement of an sPGA score of clear or almost clear at Week 16
- Achievement of an sPGA score of clear or almost clear at Week 52
- Achievement of $\geq 75\%$ reduction from baseline PASI score (PASI 75) at Week 16
- Achievement of $\geq 75\%$ reduction from baseline PASI score (PASI 75) at Week 52
- Achievement of 100% reduction from baseline PASI score (PASI 100) at Week 16
- Achievement of 100% reduction from baseline PASI score (PASI 100) at Week 52
- Achievement of an American College of Rheumatology (ACR) 20 response at Week 16
- Achievement of an ACR20 response at Week 52

5.1.3 Further Endpoints

The further endpoints are as follows:

- Achievement of $\geq 50\%$ reduction from baseline PASI score (PASI 50) at Weeks 16 and 52
- Time until the first achievement of PASI 50, PASI 75, PASI 90, PASI 100 and sPGA 0 or 1
- Time until loss of PASI 75, PASI 90, PASI 100 and sPGA 0 or 1 response
- Change from baseline in PASI score at Weeks 16 and 52
- Percent change from baseline in PASI at Weeks 16 and 52
- Absolute PASI of < 3 at all visits collected
- Achievement of an sPGA score of clear at Weeks 16 and 52
- Change from baseline in psoriasis symptoms evaluated using the total score on the Psoriasis Symptoms Scale (PSS) at Weeks 16 and 52
- Achievement of a Dermatology Life Quality Index (DLQI) score of 0 or 1 at Weeks 16 and 52
- Achievement of total score on the PSS of 0 at Weeks 16 and 52
- Change from baseline in DLQI at all Weeks 16 and 52

5.2 ASSESSMENT OF EFFICACY

The skin condition will be assessed by using the PASI, sPGA, and other relevant scores as described in Section 5.1 and the ISF.

Symptoms, quality of life, and physical function will be assessed by PSS and DLQI.

PsA assessment will be assessed by using ACR 20.

Details of the efficacy assessments are listed in [Appendix 10](#).

5.3 ASSESSMENT OF SAFETY

Safety will be assessed descriptively based on:

- Adverse events
- Serious adverse events
- Clinical laboratory values (haematology, clinical chemistry, and urinalysis)
- Intensity of AEs will be assessed by Rheumatology Common Toxicity Criteria (RCTC) version 2.0 (refer to ISF for details)

5.3.1 Physical examination

Complete and targeted physical examinations will be performed at visits as described in the [Flow Chart](#). Complete physical examination will include vital signs assessment and general appearance as well as evaluation of all relevant organ systems. Targeted physical examination will include vital signs assessment and evaluation of organ systems associated with AE(s) symptoms or laboratory abnormalities.

Clinically relevant abnormal findings will be reported as baseline conditions or AEs.

5.3.1.1 Waist circumference

Waist circumference measurements should be made around a patient's bare midriff, after the patient exhales while standing without shoes and with both feet touching and arms hanging freely. The tape should be placed perpendicular to the long axis of the body and horizontal to the floor and applied with sufficient tension to conform to the measurement surface. Waist circumference should be determined by measuring the midpoint between the lowest rib and the iliac crest.

5.3.1.2 Body Weight

Body weight measurements should be done on the same scale for each patient. In order to get comparable body weight values, it should be performed in the following way:

- fasting (except for the screening visit)
- after the urine sampling (body weight after bladder voiding)
- shoes and coat/jackets should be taken off
- pockets should be emptied of heavy objects (i.e., keys, coins, etc.)

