Statistical methods: Primary analysis: The achievement of PASI 90 at Week 16 is the primary endpoint and is binary variables with values of 0 or 1. The difference in proportion responding between the BI 655066 (risankizumab) arm and placebo arm will be estimated and tested using the Cochran-Mantel-Haenszel risk difference estimate stratified by the randomisation factors of concomitant disease of PsA at baseline (Yes versus No), and body weight (≤ 90 kg versus > 90 kg) with weights proposed by Greenland & Robins. Secondary analysis: The same methods as the primary analyses will be used to analyse all binary secondary. Change from baseline in Psoriasis Symptoms Scale (PSS) at Week 16 will be analysed by the van Elteren test between the BI 655066 (risankizumab) arm and placebo arm. In order to maintain the full significant level of 5%, two null hypotheses of each BI 655066 (risankizumab) arm vs Placebo will be tested using fixed-sequence method.			

FLOW CHART

Trial Periods	Screening	Randomised Treatment										Follow-Up		
		V2	V3	V4	V5	V6	V7	V8	V9	EOT	FU1	FU2/ EOO	FU3/ EOO	
Visit	V1													
Week			4	8	12	16	22	28	34	40	46	52	56	
Day	-42 to -14	1	29	57	85	113	155	197	239	281	323	365	393	
Visit window (days)			±3	±7	±7	±3	±7	±7	±7	±7	±7	±7	±7	
Informed consent	X													
Demographics	X													
Medical history	X													
Smoking/alcohol history	X													
Psoriasis therapy history	X													
Psoriatic arthritis history	X													
CASPAR ¹	X													
In-/exclusion criteria	X	X												
% BSA involvement	X	X												
Height	X													
Weight/waist circumference ²	X					X					X			
Physical examination ³	X _C	X _T	X _T	X _T	X _T	X _C	X _T	X _T	X _T	X _C	X _T	X _C		
Vital signs ⁴	X	X	X	X	X	X	X	X	X	X	X	X	X	
Adverse events	X	X	X	X	X	X	X	X	X	X	X	X	X	
Concomitant therapy	X	X	X	X	X	X	X	X	X	X	X	X	X	
Infection screening ⁵	X												X	
X-ray ⁵	X												X	
Pregnancy testing ⁶	X	X	X			X		X		X		X	X	
Safety laboratory tests ⁷	X	X		X		X		X		X		X		
12 lead-ECG	X	X	X			X		X		X		X		
PK sampling ⁸		X	X		X	X		X	X	X			X	
ADA sampling ⁸		X	X			X		X		X			X	
Biomarker sampling ⁹		X	X			X		X		X			X	
Local tolerability			X	X	X	X	X	X	X	X				
PASI	X	X	X	X	X	X	X	X	X	X	X	X		
sPGA	X	X				X		X		X		X		

Proprietary confidential information © 2017 Boehringer Ingelheim International GmbH or one or more of its affiliated companies

Tender and Swollen Joint Counts (TJC 68, SJC 66) ¹⁰		X			X		X		X		X

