5.3.2 Vital Signs

Vital signs evaluations will be performed at visits as shown in the Flow Chart. This includes systolic/diastolic blood pressure, pulse rate, temperature, and respiratory rate. Blood pressure, pulse rate, and respiratory rate will be measured after patients have been sitting comfortably for at least five minutes. Measurement of vital signs should precede blood sampling to avoid the impact of blood sampling on the vital measurements. At dosing visits vital signs

evaluations will be performed pre-dose and at Visit 2 and Visit 3 additional evaluations will be taken at approximately 5 minutes post-dose (5 minutes after last injection) and approximately 60 minutes post-dose (60 minutes after last injection).

Patients should be closely monitored for signs and symptoms of hypersensitivity reactions for approximately 2 hours after the last injection at Visit 2 and for approximately 1 hour after the last injection at all other visits with drug administration. Hypersensitivity reactions should be treated according to medical standards. Pre-medications for further injections might be considered and will be agreed on between investigator and BI clinical monitor.

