6.2.2 Treatment period

The treatment period is from Visit 2 to EOT Visit.

Visits 2, 4, 6, 8, EOT, and FU2/EOO will be performed in fasted state (8 hours no food and only water). If a patient comes in non-fasted where a fasting condition is required, the visit should be performed, the non-fasted condition documented on the laboratory requisition, and the patient reminded about the expected conditions.

Urine pregnancy testing for all woman of child-bearing potential will be conducted on-site prior to every dosing and must be negative to further treat the patient. A positive urine test must be confirmed with a serum pregnancy test.

Randomisation via IRT and administration of study medication should be the last activity at Visit 2.

Venipuncture (i.e., safety laboratories, PK, ADA, biomarkers) should be the last procedure prior to study drug administration.

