ITT/Safety (Part A)	RZB_75	Subjects who randomized to risankizumab 75 mg.
	RZB_150	Subjects who randomized to risankizumab 150 mg.
	PBO	Subjects who randomized to either of the two placebo arms.
ITT/Safety (Part B)	RZB_75/RZB_75	Subjects who randomized to risankizumab 75 mg.
	RZB_150/RZB_150	Subjects who randomized to risankizumab 150 mg.
	PBO/RZB_75	Subjects who randomized to placebo and then risankizumab 75 mg entered Part B
	PBO/RZB_150	Subjects who randomized to placebo and then risankizumab 150 mg entered Part B
ITT/Safety (entire study)	RZB_75/RZB_75	Subjects who randomized to risankizumab 75 mg.
	RZB_150/RZB_150	Subjects who randomized to risankizumab 150 mg.
ALL_RZB	ALL_RZB	Subjects who received at least one dose of risankizumab 75/150 mg.

5.2**Variables Used for Stratification of Randomization**

Randomization will be stratified by concomitant PsA at baseline (Yes versus No) and body weight (≤ 90 kg versus > 90 kg).

6.0**Analysis Conventions****Definition of Baseline**

The last non-missing observation collected on or before the date of the first dose of study drug injection will be used as Baseline for summary of demographics and disease characteristics, safety and efficacy analyses, with the exception that:

- The last evaluation on or prior to the date of first dose of risankizumab will be used for the safety analyses in Part B among subjects randomized to placebo at Week 0, and the safety analyses in the ALL_RZB Population.
- For all vital sign assessments, only assessments prior to first dose time will be considered, since vital signs are to be assessed both pre- and post-dose in some visits.

Entry of Part B is defined as the last non-missing observation collected on or before the date of the first dose of study drug in Part B for PBO/RZB_75 and PBO/RZB_150 arms and last non-missing observation collected on or before the date of Week 16 visit for RZB_75/RZB_75 and RZB_150/RZB_150 arms.

Definition of Final Observation (Applicable to Safety Analyses)

Final observation in Part A is defined as the last non-missing observation collected within 105 days following the last dose of study drug in Part A for those who do not enter Part B, and on or before the first dose date of study drug injection in Part B for subjects who entered Part B. For vital sign assessments, only assessments prior to the first dose of study drug injection in Part B will be included in the analysis for Part A.

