11.4.2 Statistical Methods

Changes from Baseline to each visit and to the final value in vital sign parameters will be summarized with the mean, standard deviation and median. The Baseline and final value means will also be presented for subjects who have both the Baseline and final values (see Section 6.0 for the definition of Baseline and final values).

For baseline, if there are multiple measurements on the same day, the last measurement prior to the first dose of study drug will be used as the Baseline vital sign value. If there are multiple post-baseline measurements on the same day, average value will be used.

For systolic blood pressure, diastolic blood pressure and pulse, a listing of all subjects with any vital sign value meeting criteria for potentially clinically important values will be provided. For each of these subjects, the whole course of the respective parameter will be listed. The number and percentage of subjects who have at least one value meeting criteria for potentially clinically important values will be provided for each selected vital sign parameter.

All analyses will be conducted in the Safety Population. Table for potentially clinically important vital signs will also be summarized in the ALL_RZB Population.

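### The only scheduled pre-treatment weight is exempt from fasting, which shifts weight change toward apparent loss: equally in all arms in Part A, but only in the continuous risankizumab arms in Part B

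*Protocol*

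**What the plan says.** - **Weighing rules.** Protocol Section 5.3.1.2 gives its purpose as "In order to get comparable body weight values" and then requires weighing "fasting (except for the screening visit".
- **Schedule.** By column position, the Flow Chart row "Weight/waist circumference" is marked at Visit 1 (Day -42 to -14), at Visit 6 (Week 16) and at one late visit. Visit 2 (Day 1) has no mark.
- **Day 1 vital signs.** These do not supply a weight. Protocol Section 5.3.2 defines them as follows: "This includes systolic/diastolic blood pressure, pulse rate, temperature, and respiratory rate".
- **Fasted visits.** Protocol Section 6.2.2: "Visits 2, 4, 6, 8, EOT, and FU2/EOO will be performed in fasted state". Visits 2 and 6 are on this list; screening is not.
- **Baseline.** SAP Section 6.0 uses the latest non-missing value up to first dosing with study drug. It makes an exception for patients randomised to placebo (and for the ALL_RZB analyses): "The last evaluation on or prior to the date of first dose of risankizumab will be used for the safety analyses in Part B".
- **Analysis.** SAP Section 11.4.1 lists weight among the vital sign parameters. Section 11.4.2 says: "Changes from Baseline to each visit and to the final value in vital sign parameters will be summarized", and refers back to Section 6.0 for the meaning of Baseline.

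**The concern.** The protocol sets out to make weights comparable across visits, then exempts from its fasting rule the one measurement that becomes the baseline. A weight taken after food and drink, followed by a fasted weight, gives an apparent loss with no change in the patient.

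The baseline rule then differs between groups in Part B. The continuous risankizumab groups keep the screening weight, whereas the placebo-switch groups restart from a fasted weight. The Part B table therefore sets 112 planned patients (56 + 56) whose baseline need not be fasted beside up to 56 (28 + 28) whose baseline should be. A measurement artefact could be read as an effect of longer exposure. Without a fasted pre-dose weight on the schedule, it could not be separated out afterwards.

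**Working it through.** The plan states no figure for this point, so there is none to reproduce. The check has two parts: which weight serves as baseline in each group, and how a fasting offset then carries through.

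**Baseline by group (SAP Section 6.0 applied to the Flow Chart)**

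| Group | Part A baseline | Part B baseline |
|---|---|---|
| RZB_75/RZB_75, RZB_150/RZB_150 | Screening, fasting not required | Screening, fasting not required |
| PBO/RZB_75, PBO/RZB_150 | Screening, fasting not required | Week 16, fasted |

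**Offset.** Let *f* be the share of patients not fasted at screening and *d* the weight of food and fluid in kg. Neither is in the documents; both are assumptions. If later weights are fasted, as Section 5.3.1.2 requires:

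- Part A, every arm: shift in mean change = −*f* × *d*. Screening precedes randomisation, so *f* and *d* are equal across arms in expectation, and the shift in risankizumab minus placebo is (−*fd*) − (−*fd*) = 0.
- Part B, continuous groups: −*f* × *d*.
- Part B, placebo-switch groups: 0.
- Part B gap, continuous minus switch: −*f* × *d*.

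Values of −*f* × *d* in kg:

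| *f* | *d* = 0.3 | *d* = 0.5 | *d* = 1.0 | *d* = 1.5 |
|---|---|---|---|---|
| 0 | 0 | 0 | 0 | 0 |
| 0.5 | −0.15 | −0.25 | −0.50 | −0.75 |
| 1 | −0.30 | −0.50 | −1.00 | −1.50 |

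**Late visit.** The last mark in the weight row falls under FU1 (Week 46) by column position, but the extracted table may be shifted and FU2 (Week 52) is possible. Section 6.2.2 lists FU2 as fasted and does not list FU1; Section 5.3.1.2 requires fasting for weight at either. Suppose a share *g* were unfasted at that visit. The shifts become (*g* − *f*) × *d* in the continuous groups and *g* × *d* in the switch groups. The gap between them is still (*g* − *f*)*d* − *gd* = −*fd*, so the Part B mismatch does not depend on which visit it is.

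**With a fasted Visit 2 weight as baseline.** *f* = 0 at baseline, so the offset is 0 in every group and both periods.

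**The case against.** The strongest points on the other side are these.

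- **The randomised comparison is safe.** This stands. A reader might infer that risankizumab is made to look as if it causes weight loss relative to placebo. The documents do not support that: in Part A the placebo arm has the same screening baseline and the same expected shift.
- **Screening weights may have been fasted.** This stands as a limit on size. Section 5.3.1.2 waives fasting at screening; it does not call for a fed state. It would go too far to treat every screening weight as unfasted, and the shift can be as small as zero.
- **The Part B groups are not comparable anyway.** This is partly right. The continuous groups' change includes Weeks 0 to 16 and the switch groups' does not, and the SAP's pairwise safety comparisons (Section 11.1) are risankizumab against placebo only. But the unequal period is evident from the definition, while the fasting offset is hidden inside the numbers.
- **Entry of Part B already exists.** SAP Section 6.0 defines it for all four groups, and Table 6 uses it for vital signs. However, Section 11.4.2 ties change to Baseline, so the definition does not settle the matter as written.
- **The Flow Chart was read from a damaged table.** The uncertainty is mainly about the late visit. That Visit 2 has no weight rests on column position, and Section 5.3.2 gives no other source of a Day 1 weight.
- **An amendment may come too late.** SAP Section 9.0 sets an interim cutoff of 15 December 2017. If the last patient's Week 28 visit (Day 197) fell by then, 196 days back puts the last randomisation at about 2 June 2017, or about 9 June with the 7-day window. The current protocol is dated 8 June 2017. This is an inference, but it is a good reason not to rely on the Visit 2 change alone.

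**Conclusion.** The concern holds, at minor weight. Within-arm weight change is shifted toward apparent loss in all arms in Part A, with no bias in the comparison with placebo. In Part B the shift applies only to the continuous risankizumab groups, because the baseline rule differs by group.

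The direction follows from the documents, provided that some patients were not fasted at screening and that later weights were fasted as required. The size does not follow from them. It is about 0.15 to 1.5 kg under the assumed 0.3 to 1.5 kg of food and fluid with 50 to 100% of patients unfasted, and zero if all fasted. The screening weight is also 2 to 6 weeks old at first dose, but that implies no particular direction.

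The consequence is confined to means, standard deviations and medians in a descriptive safety table. Weight is not an efficacy endpoint, and SAP Table 15 sets no clinically important criterion for it. A reader might infer that efficacy conclusions are at risk; nothing in the documents supports that.

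**What to change.** 1. **Protocol Flow Chart:** add body weight at Visit 2, before dosing. The visit is already held and already fasted, and under the existing rule in SAP Section 6.0 the value becomes the baseline without further SAP change. The cost is one scale reading per patient.
2. **SAP Section 11.4.2, for patients already past Visit 2:** also summarise Part B weight change from the Entry of Part B (Week 16) value in all four groups, alongside the change from Baseline. This puts the groups on the same kind of starting weight and the same period. The cost is one extra summary and no new data.

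Nothing more is needed for this point. Waist circumference has no fasting rule in Protocol Section 5.3.1.1 and is not in the SAP's vital sign list. The definition of the 90 kg stratum belongs to the efficacy analysis and need not be changed to repair a descriptive weight table.
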